## Bleeding on Probing by Surface

[figure not shown]

Table 6: Number of Surfaces with Bleeding on Probing

Treatment	Mean	SD	Min	Max	Median	N
1 Month						
Concave	1.097	1.2478	0	6	1	31
Divergent	1.482	1.5285	0	5	1	27
3 Months						
Concave	1.032	1.0160	0	4	1	31
Divergent	1.111	1.3960	0	5	1	27
6 Months						
Concave	1.097	1.1932	0	5	1	31
Divergent	1.000	0.9608	0	3	1	27
12 Months						
Concave	1.613	1.4532	0	6	1	31
Divergent	1.482	1.3118	0	5	1	27

Average Number of Surfaces with Bleeding on Probing

[figure not shown]

Table 7: Plaque Index

Surface	Treatment	Mean	SD	Min	Max	Median	N
1 Month							
MB	Concave	0.26	0.63	0	3	0	31
	Divergent	0.41	0.75	0	3	0	27
MIDB	Concave	0.15	0.46	0	2	0	27
	Divergent	0.14	0.47	0	2	0	22
DB	Concave	0.33	0.66	0	3	0	30
	Divergent	0.44	0.75	0	2	0	27
ML	Concave	0.39	0.72	0	3	0	31
	Divergent	0.44	0.89	0	4	0	27
MIDL	Concave	0.11	0.32	0	1	0	27
	Divergent	0.32	0.78	0	3	0	22
DL	Concave	0.52	0.72	0	3	0	31
	Divergent	0.48	0.8	0	3	0	27
Average	Concave	0.29	0.51	0	2.5	0	31
	Divergent	0.36	0.67	0	2.67	0	27
3 Months							
MB	Concave	0.26	0.58	0	2	0	31
	Divergent	0.36	0.76	0	3	0	25
MIDB	Concave	0.11	0.32	0	1	0	27
	Divergent	0.14	0.35	0	1	0	22
DB	Concave	0.23	0.56	0	2	0	31
	Divergent	0.44	0.87	0	3	0	25
ML	Concave	0.23	0.56	0	2	0	31
	Divergent	0.4	0.76	0	3	0	25
MIDL	Concave	0.07	0.27	0	1	0	27
	Divergent	0.18	0.39	0	1	0	22
DL	Concave	0.32	0.6	0	2	0	31
	Divergent	0.48	0.82	0	3	0	25
Average	Concave	0.22	0.46	0	2	0	31
	Divergent	0.33	0.6	0	2.33	0	25

Table 8: Plaque Index, continued

Surface	Treatment	Mean	SD	Min	Max	Median	N
6 Months							
MB	Concave	0.4	0.67	0	3	0	30
	Divergent	0.2	0.41	0	1	0	25
MIDB	Concave	0.1	0.31	0	1	0	30
	Divergent	0	0	0	0	0	25
DB	Concave	0.33	0.66	0	3	0	30
	Divergent	0.36	0.49	0	1	0	25
ML	Concave	0.4	0.72	0	3	0	30
	Divergent	0.24	0.44	0	1	0	25
MIDL	Concave	0.2	0.41	0	1	0	30
	Divergent	0.04	0.2	0	1	0	25
DL	Concave	0.4	0.56	0	2	0	30
	Divergent	0.44	0.51	0	1	0	25
Average	Concave	0.31	0.49	0	2	0	30
	Divergent	0.21	0.26	0	0.67	0	25
12 Months							
MB	Concave	0.56	0.58	0	2	1	27
	Divergent	0.48	0.92	0	4	0	25
MIDB	Concave	0.19	0.4	0	1	0	27
	Divergent	0.28	0.54	0	2	0	25
DB	Concave	0.74	0.71	0	3	1	27
	Divergent	0.56	0.77	0	3	0	25
ML	Concave	0.85	0.72	0	2	1	27
	Divergent	0.52	0.77	0	3	0	25
MIDL	Concave	0.26	0.45	0	1	0	27
	Divergent	0.2	0.41	0	1	0	25
DL	Concave	0.85	0.72	0	2	1	27
	Divergent	0.68	0.8	0	3	1	25
Average	Concave	0.57	0.48	0	1.67	0.67	27
	Divergent	0.45	0.62	0	2.67	0.33	25

[figure not shown]
Table 9: Gingival Index

Surface	Treatment	Mean	SD	Min	Max	Median	N
1 Month							
MB	Concave	0.52	0.57	0	2	0	31
	Divergent	0.74	0.76	0	2	1	27
MIDB	Concave	0.7	0.67	0	3	1	27
	Divergent	0.77	0.81	0	2	1	22
DB	Concave	0.55	0.62	0	2	0	31
	Divergent	0.7	0.72	0	2	1	27
ML	Concave	0.55	0.62	0	2	0	31
	Divergent	0.81	0.79	0	2	1	27
MIDL	Concave	0.56	0.58	0	2	1	27
	Divergent	0.73	0.55	0	2	1	22
DL	Concave	0.61	0.62	0	2	1	31
	Divergent	0.78	0.75	0	2	1	27
Average	Concave	0.59	0.47	0	2	0.5	31
	Divergent	0.74	0.63	0	2	0.67	27
3 Months							
MB	Concave	0.68	0.75	0	3	1	31
	Divergent	0.58	0.78	0	2	0	24
MIDB	Concave	0.59	0.57	0	2	1	27
	Divergent	0.64	0.79	0	2	0	22
DB	Concave	0.48	0.63	0	2	0	31
	Divergent	0.6	0.71	0	2	0	25
ML	Concave	0.74	0.63	0	2	1	31
	Divergent	1	0.76	0	2	1	25
MIDL	Concave	0.59	0.57	0	2	1	27
	Divergent	0.68	0.78	0	2	0.5	22
DL	Concave	0.87	0.63	0	2	1	30
	Divergent	0.96	0.79	0	2	1	25
Average	Concave	0.65	0.47	0	2	0.67	31
	Divergent	0.74	0.66	0	2	0.5	25

Table 10: Gingival Index, continued

Surface	Treatment	Mean	SD	Min	Max	Median	N
6 Months							
MB	Concave	0.67	0.61	0	2	1	30
	Divergent	0.52	0.71	0	2	0	25
MIDB	Concave	0.53	0.63	0	2	0	30
	Divergent	0.68	0.69	0	2	1	25
DB	Concave	0.7	0.6	0	2	1	30
	Divergent	0.68	0.63	0	2	1	25
ML	Concave	0.83	0.75	0	2	1	30
	Divergent	0.96	0.61	0	2	1	25
MIDL	Concave	0.6	0.62	0	2	1	30
	Divergent	0.68	0.56	0	2	1	25
DL	Concave	0.83	0.59	0	2	1	30
	Divergent	0.92	0.57	0	2	1	25
Average	Concave	0.69	0.47	0	1.83	0.67	30
	Divergent	0.74	0.43	0	1.67	0.67	25
12 Months							
MB	Concave	0.71	0.76	0	2	1	28
	Divergent	0.74	0.69	0	2	1	23
MIDB	Concave	0.71	0.6	0	2	1	28
	Divergent	0.65	0.71	0	2	1	23
DB	Concave	1.04	0.79	0	3	1	28
	Divergent	0.87	0.63	0	2	1	23
ML	Concave	1.04	0.79	0	3	1	28
	Divergent	1.04	0.77	0	2	1	23
MIDL	Concave	0.82	0.61	0	2	1	28
	Divergent	0.74	0.62	0	2	1	23
DL	Concave	1.11	0.74	0	2	1	28
	Divergent	1.39	0.66	0	2	1	23
Average	Concave	0.9	0.54	0	2.17	0.67	28
	Divergent	0.91	0.51	0.33	2	0.67	23

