# Periimplant Mucosa Dynamics Around Dynamic and Concave AtlantisTM Abutment Transition Profiles

October 1, 2019

We removed all patients without a randomized treatment and/or without any data collection. We did keep subjects with partial data in at least one of the variables. All analyses were performed using R version 3.6.0.

Table 1: Canfield

Treatment	Mean	SD	Min	Max	Median	N
Delivery						
Concave	9.770	1.146	7.46	11.67	9.86	29
Divergent	9.860	1.148	7.42	11.90	10.06	25
1 Month						
Concave	9.618	1.160	7.05	11.52	9.79	29
Divergent	9.684	1.203	7.25	11.92	9.84	25
3 Month						
Concave	9.610	1.174	6.96	11.52	9.75	29
Divergent	9.674	1.231	7.10	11.78	9.81	25
6 Month						
Concave	9.599	1.160	7.10	11.52	9.73	29
Divergent	9.652	1.166	7.27	11.56	9.80	25
12 Month						
Concave	9.596	1.167	6.91	11.45	9.70	29
Divergent	9.622	1.258	6.89	11.54	9.80	25

Average Canfield

[figure not shown]

Table 2: Geomagic

	Mean	SD	Min	Max	Median	N
Ld (Divergent)	2.5039	0.6349	1.4212	4.1078	2.457	29
Lc (Concave)	2.6484	0.6608	1.5736	4.3982	2.539	29
Δ Linear (Lc - Ld)	0.1445	0.1361	0.0122	0.6119	0.117	29
Vd (Divergent)	165.8893	41.7412	91.9577	242.6630	165.796	29
Vc (Concave)	157.9359	41.1081	88.1219	226.8050	161.692	29
Δ Volume (Vc - Vd)	-7.9534	6.1022	-21.7929	-0.2594	-6.537	29

Table 3: Probing Depth

Surface	Treatment	Mean	SD	Min	Max	Median	N
1 Month							
MB	Concave	2.68	0.65	2	4	3	31
	Divergent	2.63	0.56	2	4	3	27
MIDB	Concave	1.5	0.5	1	2	1.5	27
	Divergent	1.82	0.66	1	3	2	22
DB	Concave	2.58	0.72	2	4	2	31
	Divergent	2.85	0.77	2	4	3	27
ML	Concave	2.81	0.7	2	4	3	31
	Divergent	2.85	0.77	1	4	3	27
MIDL	Concave	1.89	0.51	1	3	2	27
	Divergent	1.86	0.77	1	3	2	22
DL	Concave	2.84	0.78	2	5	3	31
	Divergent	2.85	0.82	1	4	3	27
Average	Concave	2.42	0.4	1.67	3.17	2.5	31
	Divergent	2.53	0.45	1.67	3.25	2.5	27
3 Months							
MB	Concave	2.68	0.6	2	4	3	31
	Divergent	2.56	0.58	2	4	3	25
MIDB	Concave	1.63	0.49	1	2	2	27
	Divergent	1.75	0.61	1	3	2	22
DB	Concave	2.58	0.67	2	4	2	31
	Divergent	2.92	0.57	2	4	3	25
ML	Concave	2.84	0.86	1	5	3	31
	Divergent	3.06	0.68	2	4	3	25
MIDL	Concave	1.85	0.77	1	3	2	27
	Divergent	2.18	0.73	1	4	2	22
DL	Concave	2.94	0.73	2	4	3	31
	Divergent	3.12	0.73	2	5	3	25

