Average	Concave	2.47	0.47	1.67	3.5	2.5	31
	Divergent	2.61	0.56	1	3.67	2.67	25

Table 4: Probing Depth, continued

Surface	Treatment	Mean	SD	Min	Max	Median	N
6 Months							
MB	Concave	2.82	0.84	2	6	3	30
	Divergent	2.56	0.65	1	4	3	25
MIDB	Concave	1.57	0.57	1	3	2	30
	Divergent	1.78	0.65	1	3	2	25
DB	Concave	2.83	0.65	2	4	3	30
	Divergent	2.68	0.75	1	4	3	25
ML	Concave	2.87	0.78	1	5	3	30
	Divergent	2.92	0.49	2	4	3	25
MIDL	Concave	2.03	0.67	1	3	2	30
	Divergent	2.08	0.57	1	3	2	25
DL	Concave	3	0.83	1	5	3	30
	Divergent	3.08	0.7	2	4	3	25
Average	Concave	2.52	0.46	1.67	3.5	2.5	30
	Divergent	2.52	0.38	1.83	3.17	2.5	25
12 Months							
MB	Concave	2.8	0.72	2	5	3	28
	Divergent	2.76	0.97	2	6	3	25
MIDB	Concave	1.54	0.58	1	3	1.5	28
	Divergent	1.84	0.69	1	4	2	25
DB	Concave	2.89	0.82	2	6	3	28
	Divergent	2.96	0.61	2	4	3	25
ML	Concave	2.96	0.79	2	5	3	28
	Divergent	3.2	0.87	2	5	3	25
MIDL	Concave	2	0.61	1	3	2	28
	Divergent	2.12	0.88	1	5	2	25
DL	Concave	3.11	0.88	2	6	3	28
	Divergent	3.16	0.69	2	5	3	25
Average	Concave	2.55	0.5	1.67	4	2.54	28
	Divergent	2.67	0.54	1.67	4	2.83	25

[figure not shown]

Table 5: Bleeding on Probing

Surface	Time	Concave	Divergent
MB	1 Month	25.81%	29.63%
	3 Months	22.58%	11.11%
	6 Months	19.35%	11.11%
	12 Months	22.58%	18.52%
MIDB	1 Month	25.81%	29.63%
	3 Months	6.452%	25.93%
	6 Months	22.58%	18.52%
	12 Months	29.03%	22.22%
DB	1 Month	9.677%	14.81%
	3 Months	6.452%	22.22%
	6 Months	12.9%	14.81%
	12 Months	25.81%	22.22%
ML	1 Month	25.81%	29.63%
	3 Months	35.48%	22.22%
	6 Months	12.9%	14.81%
	12 Months	19.35%	33.33%
MIDL	1 Month	9.677%	14.81%
	3 Months	12.9%	7.407%
	6 Months	22.58%	14.81%
	12 Months	29.03%	14.81%
DL	1 Month	12.9%	29.63%
	3 Months	19.35%	22.22%
	6 Months	19.35%	25.93%
	12 Months	35.48%	37.04%

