### Average Plaque Index

### Average Gingival Index

[figure not shown]

Table 11: Bucco-Lingual Thickness

Treatment	Mean	SD	Min	Max	Median	N
Baseline						
Concave	2.814	1.1291	1.0	6.0	2.50	31
Divergent	2.722	1.1294	1.0	6.0	2.50	27
1 Month						
Concave	2.597	0.6248	1.0	4.0	2.50	31
Divergent	2.667	0.6202	1.5	4.0	2.50	27
3 Months						
Concave	2.468	0.5764	1.5	3.5	2.50	31
Divergent	2.840	0.7176	1.5	4.0	3.00	25
6 Months						
Concave	2.517	0.5796	1.5	3.5	2.50	30
Divergent	2.920	0.6403	1.5	4.5	3.00	25
12 Months						
Concave	2.500	0.5000	2.0	4.0	2.50	29
Divergent	2.740	0.7654	1.5	4.0	3.00	25
Average						
Concave	2.594	0.4731	1.9	3.7	2.55	31
Divergent	2.785	0.5159	1.8	3.7	2.80	27

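### Bleeding Tables 5 and 6 use denominators of 31 and 27 at every visit; in 36 of 48 surface-by-visit cells this exceeds the number with a probing depth, and no coding rule is given

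*Combined protocol and SAP*

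**What the plan says.** The protocol lists change in bleeding on probing among its secondary objectives (Study objectives). It plans to score bleeding and probing depth at the same six sites (Outcome variables).

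In the October 1, 2019 report:

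- "Table 5: Bleeding on Probing" gives percentages by surface and visit without an N.
- "Table 6: Number of Surfaces with Bleeding on Probing" gives N = 31 concave and 27 divergent at 1, 3, 6 and 12 months.
- "Table 3: Probing Depth" and "Table 4: Probing Depth, continued" give the number with a probing depth for each surface, visit and arm. It is lower than 31 and 27 in most places.
- The only data-handling statements are that subjects with no randomized treatment or no data were removed, and "We did keep subjects with partial data in at least one of the variables". The protocol's Statistical methods section adds only that the mixed model can cope with missing data. Neither says how a blank bleeding score is coded.
- The Statistical Analyses section counts bleeding among the outcomes that changed significantly over time. Table 15 gives p = 0.0282 for the squared time term and p = 0.9170 for treatment.

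**The concern.** Bleeding on probing is read when a site is probed, so its denominators should follow those of probing depth closely. Here they never move, while every other recall measure loses divergent subjects after 1 month, or has only 25 throughout in the case of the Canfield photographs. A yes/no item that alone shows no missing data suggests that blanks were read as "no".

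If that happened, bleeding is understated, and unevenly by arm, surface and visit, because the missing data are uneven. The report does not say whether the models in Tables 15 and 22 used the same counts, so a reader cannot tell how many observed sites support the reported time effect.

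**Working it through.** **1. Reproduce Tables 5 and 6.** For each Table 5 percentage, find a whole number k with 100·k/n equal to the printed value to four significant figures. Example, mid-buccal at 3 months: 2/31 = 6.452% and 7/27 = 25.93%, as printed. Of the denominators 15 to 59, only 31 fits all 24 concave cells, and only 27 or its double, 54, fits all 24 divergent cells.

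Summing k over the six surfaces and dividing by 31 or 27 returns every Table 6 mean:

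| | 1 mo | 3 mo | 6 mo | 12 mo |
|---|---|---|---|---|
| Concave total | 34 | 32 | 34 | 50 |
| Total / 31 | 1.097 | 1.032 | 1.097 | 1.613 |
| Divergent total | 40 | 30 | 27 | 40 |
| Total / 27 | 1.481 (printed 1.482) | 1.111 | 1.000 | 1.481 (printed 1.482) |

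The Table 6 SDs agree. The sum of squares is (N − 1)·SD² + total²/N. At 12 months this is 30 × 1.4532² + 50²/31 = 144 (concave) and 26 × 1.3118² + 40²/27 = 104 (divergent). The other six rows also give whole numbers.

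**2. Compare with the number having a probing depth (Tables 3 and 4).**

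| | 1 mo | 3 mo | 6 mo | 12 mo |
|---|---|---|---|---|
| Concave, four interproximal surfaces | 31 | 31 | 30 | 28 |
| Concave, mid-buccal and mid-lingual | 27 | 27 | 30 | 28 |
| Concave cells below 31 | 2 | 2 | 6 | 6 |
| Divergent, four interproximal surfaces | 27 | 25 | 25 | 25 |
| Divergent, mid-buccal and mid-lingual | 22 | 22 | 25 | 25 |
| Divergent cells below 27 | 2 | 6 | 6 | 6 |

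That makes 16 + 20 = 36 of 48 cells. In none of the 36 does a whole count over the probing-depth N give the printed percentage. By subject, five of the eight Table 6 rows exceed the number with any probing depth: concave at 6 and 12 months, and divergent at 3, 6 and 12 months.

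Sites with a depth = 4 × interproximal N + 2 × mid-surface N:

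- Concave: 178 + 178 + 180 + 168 = 704.
- Divergent: 152 + 144 + 150 + 150 = 596.
- Together 1,300, against 6 × 4 × (31 + 27) = 1,392 for bleeding, a difference of 92.

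**3. Compare with the other measures.** After 1 month, no other clinical or photographic table has more than 25 divergent subjects. At 12 months the concave N is 29 in "Table 11: Bucco-Lingual Thickness", 28 for probing depth and 27 in "Table 8: Plaque Index, continued". The divergent N is 23 in "Table 10: Gingival Index, continued" and 25 elsewhere.

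**4. Size, if missing was coded as zero and no bleeding was recorded at unexamined sites.**

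- 12-month means: concave 50/29 = 1.724, 50/28 = 1.786, 50/27 = 1.852; divergent 40/25 = 1.600, 40/23 = 1.739.
- Share of sites at 12 months: concave 50/186 = 26.9% becomes 28.7% (50/174) to 30.9% (50/162). Divergent 40/162 = 24.7% becomes 26.7% (40/150) to 29.0% (40/138).
- 12-month arm gap as printed: 1.613 − 1.482 = 0.131, SE √(1.4532²/31 + 1.3118²/27) = 0.36. On probing-depth Ns: 1.786 − 1.600 = 0.186. Over all N combinations: 1.724 − 1.739 = −0.015 to 1.852 − 1.600 = 0.252. Removing zero counts gives SDs of 1.41–1.44 and 1.25–1.29 and an SE of about 0.37, so |t| is at most 0.252/0.374 = 0.67.
- All visits pooled, share of sites: concave 150/744 = 20.2% becomes 150/704 = 21.3%; divergent 137/648 = 21.1% becomes 137/596 = 23.0%.
- Largest single cell, divergent mid-buccal at 1 month: 8/27 = 29.6% becomes 8/22 = 36.4%.
- Rise from 1 to 12 months, arms pooled: as printed 74/348 = 21.3% to 90/348 = 25.9%, or 4.6 points. On probing-depth Ns 74/330 = 22.4% to 90/318 = 28.3%, or 5.9 points.

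**5. Separate check on Table 3.** The divergent 3-month average probing depth has a printed minimum of 1 with N = 25. All four interproximal surfaces have N = 25 and a minimum of 2 mm; the two mid surfaces have a minimum of 1 mm. No subject's average can be below (4 × 2 + 2 × 1)/6 = 1.67, or 2.0 where only the four interproximal sites were recorded.

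**The case against.** The strongest reply is that Tables 3 and 4 count recorded depths, not sites examined for bleeding, and no N for the latter is printed. Bleeding may have been noted where no depth was written down, or earlier values carried forward. Ns already differ between measures in this report, and the Canfield table has a constant N too, so a constant or different N is not in itself an error. This stands as a limit on the cause. It does not explain why bleeding alone exceeds every other recall measure: by two divergent subjects from 3 months on, and by at least two concave subjects at 12 months.

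Six of the 36 cells (the two mid surfaces at 1 month in both arms and at 3 months in the concave arm) occur where the subject-level N agrees, so a missed visit cannot account for them. They conflict only if the mid sites were not examined for bleeding. The largest-cell figure depends on this, as does the pooled rise: excluding only subjects with no depth at all gives 74/348 to 90/318, a rise of 7.0 points instead of 5.9. The ends of the 12-month range also borrow Ns from different measures. These are fair reasons to read the magnitudes as conditional ranges.

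Finally, nothing is shown to reverse. Table 22, whose model needs thickness (available at 223 of the 232 subject-visits), still gives p = 0.0381 for the squared time term. That is only partial reassurance: it assumes rows without thickness were dropped, and that model has thickness in place of treatment.

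**Conclusion.** The concern holds and should be fixed. The fixed denominators of 31 and 27 are printed in Table 6 and forced by the arithmetic in Table 5. They conflict with the report's own probing-depth Ns in 36 of 48 cells, and no rule explains them. Confidence is high on that point only.

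That missing scores were counted as no bleeding is an inference. If it is right, and no bleeding was recorded at unexamined sites, the 12-month means are too low by about 0.11–0.24 surfaces (concave) and 0.12–0.26 (divergent). The arm difference stays well within its error, and the rise over time becomes somewhat larger. The absence of a treatment effect on bleeding is not put in doubt, and the primary outcome is not involved. The printed minimum of 1 for the divergent 3-month average depth is a separate error and does not depend on that inference.

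**What to change.** 1. Check in the data and code how blank bleeding entries were handled.
2. If they were set to zero, set unexamined sites and missed visits to missing. Recompute Tables 5 and 6 with sites examined as denominators, print N by surface and visit, and rerun the models in Tables 15 and 22 if they used the filled counts.
3. If another rule produced 31 and 27, state it and reconcile it with the Ns in the other tables.
4. Correct the divergent 3-month minimum average probing depth and recheck that row's mean and SD.

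The first step is a data check. If zeros were filled, the cost is a recode and a rerun of secondary analyses, with bleeding figures slightly less favourable than printed. If not, one sentence stating the rule and its reconciliation settles the bleeding tables.

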### Average Plaque Index

### Average Gingival Index

[figure not shown]

Table 11: Bucco-Lingual Thickness

Treatment	Mean	SD	Min	Max	Median	N
Baseline						
Concave	2.814	1.1291	1.0	6.0	2.50	31
Divergent	2.722	1.1294	1.0	6.0	2.50	27
1 Month						
Concave	2.597	0.6248	1.0	4.0	2.50	31
Divergent	2.667	0.6202	1.5	4.0	2.50	27
3 Months						
Concave	2.468	0.5764	1.5	3.5	2.50	31
Divergent	2.840	0.7176	1.5	4.0	3.00	25
6 Months						
Concave	2.517	0.5796	1.5	3.5	2.50	30
Divergent	2.920	0.6403	1.5	4.5	3.00	25
12 Months						
Concave	2.500	0.5000	2.0	4.0	2.50	29
Divergent	2.740	0.7654	1.5	4.0	3.00	25
Average						
Concave	2.594	0.4731	1.9	3.7	2.55	31
Divergent	2.785	0.5159	1.8	3.7	2.80	27

### Average Bucco-Lingual Thickness

[figure not shown]
[figure not shown]

Table 12: Keratinized Mucosa Width

Treatment	Mean	SD	Min	Max	Median	N
Baseline						
Concave	3.307	1.8425	0.0	9.0	3.0	31
Divergent	2.704	1.1373	0.0	5.0	3.0	27
1 Month						
Concave	3.936	1.7212	2.0	9.0	3.5	31
Divergent	3.407	1.1522	0.0	5.0	3.5	27
3 Months						
Concave	4.177	1.6711	2.0	9.0	4.0	31
Divergent	3.620	0.8930	2.0	5.0	4.0	25
6 Months						
Concave	4.067	1.6439	2.0	8.0	3.5	30
Divergent	3.478	0.9946	1.5	5.5	3.5	25
12 Months						
Concave	4.035	1.8609	1.0	9.0	3.5	29
Divergent	3.560	1.0832	1.0	5.5	4.0	25
Average						
Concave	3.878	1.6421	1.4	8.4	3.4	31
Divergent	3.257	1.0644	0.0	4.7	3.3	27

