A unified repeated measures analysis (11,12) will be used to describe the time course and to assess the effects of divergent vs. concave abutment design. This approach will make it possible to take into account the correlation of repeated measures on a given subject over time, and to consider the impact of abutment type, as well as other potential covariates. Subject will be treated as a random effect and other factors as fixed effects. Candidate covariate effects that will be explored include sex, age, history of periodontal disease, tooth position, clinical crown anatomy and the condition of adjacent teeth. So as not to exceed the limitations of sample size, we will first consider the relationship of each candidate with the outcome separately, and incorporate those with promising relationships into subsequent modeling. Parameters will be estimated using restricted maximum likelihood

(REML) methods, and a variety of different variance-covariance structures will be entertained, as appropriate. These approaches can accommodate missing data and possible time-dependency of the covariate, both of which may be relevant to this situation. Appropriateness of assumptions associated with the modeling, such as normality, will be fully assessed, and normalizing transformations considered as appropriate. Should these approaches not appear feasible, nonparametric methods for longitudinal data (13, 14) will be considered.

Comparisons of tissue alterations between the two abutments types at each follow-up time are also of interest: Changes relative to baseline will be compared at each of the four recall time points, initially using either the two-sample Student's t-test to compare abutment types, or its nonparametric analog, the Wilcoxon rank sum test, as appropriate. In addition, standard linear modeling will be used to incorporate the possible impact of other covariates. Adjustment for multiple comparisons will be made using the modified Bonferroni method due to Holm (15) in conjunction with an overall Type I error of 0.05.

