### Baseline-adjusted Analysis

We adjusted for baseline values of Canfield, bucco-lingual thickness, and keratinized mucosa width by subtracting the baseline from each subsequent measure, since any differences at delivery for these variables should be due to chance and not implant type.

Table 24: Canfield (Adjusted for Baseline)

Treatment	Mean	SD	Min	Max	Median	N
1 Month						
Concave	-0.152	0.180	-0.74	0.09	-0.15	29
Divergent	-0.176	0.302	-0.73	0.73	-0.14	25
3 Month						
Concave	-0.160	0.242	-0.89	0.54	-0.15	29
Divergent	-0.185	0.329	-0.91	0.71	-0.17	25
6 Month						
Concave	-0.171	0.280	-0.99	0.54	-0.15	29
Divergent	-0.207	0.323	-0.74	0.72	-0.23	25
12 Month						
Concave	-0.174	0.278	-0.84	0.54	-0.20	29
Divergent	-0.238	0.362	-0.85	0.75	-0.31	25

Average Canfield (Adjusted for Baseline)

[figure not shown]

Table 25: Bucco-Lingual Thickness (Adjusted for Baseline)

Treatment	Mean	SD	Min	Max	Median	N
1 Month						
Concave	-0.218	1.138	-3.5	2.0	0.0	31
Divergent	-0.056	1.204	-3.5	2.0	0.0	27
3 Months						
Concave	-0.347	1.030	-3.0	1.5	0.0	31
Divergent	0.120	1.244	-2.5	3.0	0.0	25
6 Months						
Concave	-0.258	1.175	-4.0	2.0	0.0	30
Divergent	0.200	1.199	-3.5	2.0	0.5	25
12 Months						
Concave	-0.267	1.250	-3.5	2.0	0.0	29
Divergent	0.020	1.036	-2.0	2.5	0.0	25

Average Bucco-Lingual Thickness (Adjusted for Baseline)

[figure not shown]
[figure not shown]

Table 26: Keratinized Mucosa Width (Adjusted for Baseline)

Treatment	Mean	SD	Min	Max	Median	N
1 Month						
Concave	0.629	1.056	-1	4.0	0.5	31
Divergent	0.704	0.737	0	2.0	0.5	27
3 Months						
Concave	0.871	1.162	-2	4.0	1.0	31
Divergent	0.800	0.890	-1	2.5	1.0	25
6 Months						
Concave	0.717	1.031	-1	4.0	0.5	30
Divergent	0.658	0.863	-1	2.0	0.5	25
12 Months						
Concave	0.672	1.144	-3	4.0	1.0	29
Divergent	0.740	0.914	-1	2.0	1.0	25

Average Keratinized Mucosa Width (Adjusted for Baseline)

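### The six-month divergent keratinized-width row (mean 3.478, SD 0.9946, N 25) cannot come from 25 probe readings; one or more entries need checking against source

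*Combined protocol and SAP*

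**What the plan says.** Table 12 of the statistical report gives mean, SD, minimum, maximum, median and N of keratinized mucosa width by arm and visit. For the divergent arm at six months it prints "Divergent 3.478 0.9946 1.5 5.5 3.5 25". The neighbouring visits of the same arm are "Divergent 3.620 0.8930 2.0 5.0 4.0 25" (3 months) and "Divergent 3.560 1.0832 1.0 5.5 4.0 25" (12 months).

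Table 26 gives the change from baseline for the same arm: "Divergent 0.800 0.890 -1 2.5 1.0 25" at 3 months, "Divergent 0.658 0.863 -1 2.0 0.5 25" at 6 months and "Divergent 0.740 0.914 -1 2.0 1.0 25" at 12 months.

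On missing data, the opening paragraph of the report says only: "We did keep subjects with partial data in at least one of the variables". It describes no imputation. The protocol, under Statistical methods, plans REML mixed models and remarks: "These approaches can accommodate missing data". Under Materials and method it says that keratinized width is read with a UNC-style probe. It does not state the reading step.

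**The concern.** A periodontal probe gives readings in coarse steps, so the sum of 25 readings must fall on the same steps. The sum implied by this row does not. One or more of the 25 values therefore does not look like a probe reading.

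What is at stake depends on the cause. If values were filled in, they are counted as observations, the printed spread is too small, and the report does not disclose the fill. If an entry was mis-keyed, the row needs only a small correction. In either case a printed figure is wrong, and the value has probably entered the keratinized-width models.

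**Working it through.** **Inputs.** Means, SDs and Ns from Tables 11, 12 and 26. The 0.5 mm step is an assumption drawn from the printed values and the other rows.

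**Method.** For N readings on a step g, the sum must be a multiple of g, and the sum of squares a multiple of g² with matching parity. Both must reproduce the printed mean and SD. Rounding to three decimals was allowed, directly or by way of four decimals, because other rows show the latter (102.5/31 is printed as 3.307).

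**Step 1: the other rows reproduce.** Tables 11 and 12 hold 20 arm-by-visit rows. Eighteen reproduce in mean and SD on the 0.5 mm step at their printed N. Concave baseline thickness (2.814, N 31) reproduces with a quarter-millimetre value. In the divergent keratinized-width rows, 25 × 3.620 = 90.5 at 3 months and 25 × 3.560 = 89.0 at 12 months.

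**Step 2: this row does not.** 25 × 3.478 = 86.95.
- 0.5 mm step: 86.5/25 = 3.460 and 87.0/25 = 3.480.
- 0.25 mm step: 86.75/25 = 3.470 and 87.0/25 = 3.480.
- 0.1 mm step: 86.9/25 = 3.476 and 87.0/25 = 3.480.

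None gives 3.478.

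**Step 3: it is not a misprint in one cell.** Table 26 gives the baseline sum of the 25 subjects twice: 90.5 − 25 × 0.800 = 70.5 and 89.0 − 25 × 0.740 = 70.5. The six-month change then implies a six-month sum of 70.5 + 25 × 0.658 = 86.95 again. A sum of 87.0 would have printed (87.0 − 70.5)/25 = 0.660.

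**Step 4: explanation (a), 23 readings plus two arm-mean fills.** Numbers of genuine readings from 10 to 25 were tried, with the rest set to their mean. Only 23 fits.
- Sum 80.0, so the mean is 80/23 = 3.4783.
- Sum of squares 302.0, so SS = 302 − 6400/23 = 23.739.
- Two values at the mean add nothing to SS: SD = √(23.739/24) = 0.99455, printed 0.9946.
- Without the fills: SD = √(23.739/22) = 1.039 and SE = 1.039/√23 = 0.217, against 0.9946/√25 = 0.199 as printed.
- Mean change: (25 × 80/23 − 70.5)/25 = 0.6583, printed 0.658.
- The Table 26 SD of 0.863 reproduces if the two subjects' baselines sum to 6.0 mm.

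A plain misprint of N does not fit. With sum 80.0, 23 readings give SD 0.9941 or 1.0054 on either side of the printed 0.9946.

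**Step 5: explanation (b), one off-grid entry among 25.** Take 24 half-millimetre readings with sum 83.5 and sum of squares 314.25, plus one entry of 3.45.
- Mean (83.5 + 3.45)/25 = 3.478.
- SS = 314.25 + 3.45² − 86.95²/25 = 326.1525 − 302.4121 = 23.7404; SD = √(23.7404/24) = 0.99458, printed 0.9946. Entries of 3.44 and 3.46 also pass.
- Mean change (86.95 − 70.5)/25 = 0.658. The Table 26 SD reproduces as 0.8631 if this subject's baseline was 3.0 mm.
- If the true reading was 3.5: mean 87.0/25 = 3.480; SS = 326.5 − 87²/25 = 23.74; SD = √(23.74/24) = 0.9946; mean change 0.660; N still 25.

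**Step 6: the Average row does not separate them.** It is printed as 3.257 (N 27). Both explanations reproduce it on the same assumed one-month readings for the two subjects who leave the arm after that visit (sum 3.0 mm): 3.2571 under (a) and 3.2570 under (b).

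**The case against.** The strongest objection is that fill-in is only inferred. A single entry near 3.45 mm fits every printed mean and SD that was checked, and under that explanation N and SD are right as printed. The mean change of 0.658 does not favour fill-in either, since any six-month sum near 86.95 gives it. The match to the Table 26 SD rests on baselines that are not printed. Pairs of off-grid entries, such as 3.25 with 4.7, also reproduce the Table 12 mean and SD. The reading step is itself inferred, and concave baseline thickness shows that an off-grid value can occur elsewhere. All of this stands. Against it, an entry of 3.45 needs a resolution finer than any other row requires, and a quarter-millimetre step does not rescue this row.

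A reader might infer that missing data were handled differently in the two arms, because concave N falls from 31 to 30 to 29 while this row stays at 25. The documents do not support that. The divergent arm also leaves values missing: keratinized width falls from 27 to 25, and the 12-month Gingival Index has N 23. Bucco-lingual thickness at the same visit prints N 25 and reproduces on the 0.5 mm step. Fill-in would have to be confined to one variable at one visit, which only the source data can show.

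**Conclusion.** The point holds in limited form. The row is inconsistent with 25 readings in 0.5, 0.25 or 0.1 mm steps, and Table 26 shows that the discrepancy lies in the analysed data and not just in one printed cell. That the models used the same values is likely but not stated.

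A reader might go further and conclude that N is overstated and the SD too small. That follows only under explanation (a), where the printed SD is about 4% and the standard error about 8% too small, with the mean unchanged. Under (b), with a true reading of 3.5, the mean moves by 0.002 mm and N and SD stand. The documents cannot decide between them.

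The effect is small either way. Keratinized width is a secondary outcome, and the treatment results (p 0.106 in Table 19, p 0.952 in Table 29) are not expected to change in meaning.

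**What to change.** Scan the 25 six-month divergent keratinized-width values for any that are off the 0.5 mm step, and check those records against source. Then:
- If values were filled in, set them to missing and print the row with the observed N and SD (23 and 1.039 if there were two arm-mean fills).
- If an entry was mis-keyed, correct it and print the resulting mean (3.480 if the reading was 3.5).
- Reprint the row in Tables 12 and 26, including the Average row of Table 12 if it changes, and rerun Tables 19, 23 and 29 on observed readings only. The planned REML model allows this without any fill.
- Add one sentence to the report on how missing readings were handled.

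The cost is a look-up of probably one or two records and a rerun of existing code. If fills are confirmed, the price is a slightly larger SD.
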